4.1 Number of cases

A total of 106 patients needed to be enrolled.

4.2. Inclusion Criteria

- 1) Age 18-75 years;
- 2) Meet the diagnostic criteria of China's "Guidelines for Diagnosis and Treatment of Primary Liver Cancer (2022 Edition)", clinically diagnosed with primary liver cancer, hospitalized with radical hepatectomy as the main surgical treatment, no indication of metastasis of the tumor to extra-hepatic organs in preoperative tests and examinations, no absolute contraindications to surgery, complete resection of the liver tumor in the operation, and hepatocellular carcinoma confirmed by postoperative pathological diagnosis;
3. Child-Pugh grades A and B;
- 4) Preoperative Eastern Cooperative Oncology Group Physical Status Score (ECOG-PS) of 0 to 2;
- 5) The patient is conscious, has normal verbal communication, and is able to cooperate with the relevant examinations;
- 6) Fully informed about the study and voluntarily signed an informed consent form.

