The 2022 Guidelines for Perioperative Care in Liver Surgery: the Accelerated Rehabilitation After Surgery Society (ERAS) recommends early intake after hepatic resection and oral nutritional supplements for malnourished patients ^[14]. However, for patients with abnormal liver function or cirrhosis their perioperative and postoperative nutritional support and nutritional support patterns lack guideline recommendations. Abnormal liver function and inadequate intake in postoperative patients cause patients to exhibit reduced hepatic glycogen reserves, enhanced gluconeogenesis and fat oxidation, and increased protein oxidative catabolism. To mitigate accelerated starvation and associated protein hydrolysis, the most critical dietary strategy is to eat meals every 4 to 6 hours with the shortest possible interval between meals. Therefore, the concept of Late evening snack (LES), in which a portion of food is moved to bedtime while the total daily intake remains unchanged, has been proposed to effectively improve the metabolic state of accelerated catabolism and has been recommended by the European Society of Clinical Nutrition and Metabolism (ESPEN) for patients with cirrhosis who have a high catabolic metabolism^[15], without indicating the specific nutritional composition, while the International Society for Hepatic Encephalopathy and Nitrogen Metabolism recommended in its consensus published in 2013^[16] that LES should contain at least 50 g of complex carbohydrates. In most studies, various combinations of LES (200-275 kcal total calories, 11.5g-18g protein, and 25-55g complex carbohydrates) have been shown to be significant in improving liver function indices and nutritional indices ^[17]. Researchers have suggested that LES containing complex carbohydrates and proteins may reduce lipid oxidation and improve nutritional status, muscle mass, liver function and quality of life in patients ^[18,19].

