The results of a study in an outpatient long-term late-evening snacks also confirmed a significant improvement in nitrogen balance compared to baseline and an increase in serum albumin levels ^[20]. In a meta-analysis published in 2018 ^[19], serum albumin, prealbumin, and cholinesterase levels were significantly elevated in patients with cirrhosis after implementation of LES. In addition, Chen et al ^[17] found that LES reduced the levels of alanine aminotransferase (ALT), alanine aminotransferase (AST), prothrombin time (PT), and blood ammonia in patients with liver disease, and reduced the incidence of ascites. With further research, Takeshita et al ^[21] found that LES prevented the decline of albumin levels in hepatocellular carcinoma patients undergoing chemoembolization therapy (TACE) and reduced hepatic impairment due to TACE. Meanwhile, Harima et al ^[22] showed that LES improved prealbumin levels,

BCAA/tyrosine, and ALT in patients with advanced hepatocellular carcinoma treated with hepatic artery perfusion chemotherapy. In addition, Morihara et al [23] found that LES also significantly improved Child-Pugh score in hepatocellular carcinoma patients at 4 and 12 weeks after radiofrequency ablation.

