3.1 Types of Research Designs

Types of study designs: single-center, prospective cohort studies

Research Center: Drum Tower Hospital, Medical School of Nanjing University

Grouping method: non-randomized, open, enrolled according to patients' wishes

[figure not shown]
Sample size calculation basis and formula:

This study was a single-center prospective cohort study with two groups, the test group and the control group, and the serum albumin level of the study subjects was the primary endpoint outcome indicator observed. Based on the review of previous literature^[28] and reference to the results of the pretest, it was expected that the albumin level before LES intervention was 34.2 ± 3.9 g/L and the albumin level

after LES intervention was 37.5 ± 5.4 g/L, with a two-sided $\alpha=0.05$ and a degree of certainty of $1-\beta=90\%$. Using PASS15 software can be calculated to obtain $n=88$ cases. Based on the 1:1 grouping, 44 subjects were needed in each of the test and control groups, and assuming a 20% subject dropout rate, the final minimum number of subjects needed was 53 in each of the test and control groups, for a total of at least 106 subjects included.

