3.2 Experimental Steps

The specific steps of the study are as follows:

Pre-procedure preparation:

According to the literature research, establish the form of patients' clinicopathological data that need to be collected, including basic information (age, gender, hospitalization number), pre-surgical laboratory examination (nutritional indexes, liver function, renal function, coagulation function, blood routine, tumor markers such as alpha-fetoprotein, etc.), surgical records (tumor location, size, number, intra-operative bleeding, etc.), post-surgical laboratory examination, tumor recurrence and treatment modality and patient survival, etc., as well as the establishment of a dietary matching table, respectively writing the dietary education content of the experimental group and the control group, in order to personalize the guidance of the patient's postoperative diet and the correct understanding of the importance of dietary therapy. A case questionnaire was set up for the enrolled patients, and the relevant data of the enrolled patients were recorded in the form.

Screening and Trial:

Patients who were admitted to the Department of Hepatobiliary Pancreatic Surgery of Drum Tower Hospital affiliated to Nanjing University School of Medicine, from February 2024 to January 2025 and met the enrollment criteria were selected for inclusion in this study. The grouping was not randomized and blinded, and all patients were enrolled according to their individual wishes and divided into a test group (53 cases) and a control group (53 cases). The purpose of the study, the content of the investigation, the principle of confidentiality were explained to the patients or their families at the time of their admission to the hospital to reduce the concerns of the respondents, and the subjects were included in the study after signing the informed consent form with their consent.

1. Treatment program:

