(2) Postoperative: start drinking small amount of water on the 1st postoperative day, over to liquid diet after ventilation, and may over to autonomous semi-liquid diet + oral whole protein enteral nutrition during the day + LES program on the 2nd postoperative day. As the patient's voluntary intake meets 60% of the body's needs, the daytime oral enteral nutrition support can be gradually stopped and the LES program can be continued.

3) Discharge: daily intake needs to be on time according to the LES regimen.

Control group: no more food 1h before bedtime.

(1) Preoperative: same as the test group.

(2) Postoperative: start drinking small amount of water on the 1st postoperative day, over to liquid diet after ventilation, and can over to autonomous semi-liquid diet + oral whole protein type enteral nutrition during the day on the 2nd postoperative day. As the patient's voluntary intake meets 60% of the body's needs, enteral nutrition support can be gradually stopped.

(3) Discharge: Doctors judge whether the patients need to continue nutritional support according to their dietary recovery, and if they do, their nutritional supplementation should be completed before 1h

before bedtime.

2. biological sample collection:

Serum samples remaining after testing were collected from patients for metabolomics analysis.

3.Clinical information collection:

(1) General information collection: gender, age, height, weight, BMI, ICG15min retention time, name of surgery, duration of surgery, blood loss, blood transfusion, tumor stage, NRS2002, PG-SGA, GLIM malnutrition assessment (diagnosis) criteria diagnosis;

(2) Nutritional indicators collection: collect nutritional indicators such as serum albumin (ALB), prealbumin (PA), transferrin (TRF), and total serum protein (TP) on the 1st day of the subject's admission to the hospital, on the 6th day of the postoperative period, at 1 month after the operation, at 3 months after the operation, and at 6 months after the operation.

(3) Collection of liver function indexes: Liver function indexes such as alanine aminotransferase (ALT), alanine grass aminotransferase (AST), γ -glutamyltransferase (GGT), cholinesterase (CHE), and total bilirubin (TBIL) were collected on the first day of hospitalization, the sixth postoperative day, the first postoperative month, the third postoperative month and the sixth postoperative month of the subjects.

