4.3 Exclusion Criteria

- 1) Failure to meet selection criteria;
- 2) Nutritional assessment as cachexia;
- 3) Presence of contraindications to enteral nutrition (EN) or EN intolerance, such as acute gastrointestinal bleeding, intestinal obstruction. (\geq grade 3, National Cancer Institute-Common Terminology Criteria for Adverse Events [NCINCI-CTCAE v 5.0]);
- 4) Simultaneous combination of malignant tumors in other parts of the body;
- 5) Combined hepatic encephalopathy or definite infection on admission;
- 6) Known refractory metabolic diseases (e.g., poorly controlled diabetes mellitus or fasting glucose \geq 10 mmol/L, hyperthyroidism, hypothyroidism, metabolic acidosis);
- 7) Decreased renal function (defined as serum creatinine Cr level \geq 176.8 μ mol/L);
- 8) Intravenous or oral nutritional supplements, such as proteins, amino acids, etc., applied within one month prior to admission to the hospital;
- 9) Patients with severe stress or severe complications such as respiratory failure with severe cardiac,

hepatic, renal and other insufficiencies;

- 10) Persons with mental and neurological disorders who are unable to cooperate with a physician;
- 11) Alzheimer's disease, cerebral atrophy, acute stage or sequelae of cerebrovascular disease, cognitive impairment;
- 12) Previously poor adherence to medication and nutritional counseling;
- 13) Critically ill and difficult to assess;
- 14) On the liver transplant waiting list or under consideration for liver transplantation, as such patients may discontinue follow-up before the end of the study;
- 15) Less than 12 months since last localized treatment (TACE or HAIC or ablative therapy);
- 16) Other circumstances that the researcher considers inappropriate for participation in the study.

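### Cirrhosis is not named for recording or adjustment, so an imbalance between the self-selected groups would bias the albumin comparison unseen

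*Combined protocol and SAP*

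**What the plan says.** **Eligibility.** The only criterion on liver reserve in section 4.2 is "Child-Pugh grades A and B". The nearest exclusion in section 4.3 is "Combined hepatic encephalopathy or definite infection on admission". Neither these sections nor section 4.4 mentions cirrhosis.

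**Data to be collected.** The general information in section 3.2 covers "gender, age, height, weight, BMI, ICG15min retention time, name of surgery, duration of surgery, blood loss, blood transfusion, tumor stage", followed by nutritional scores. The case form described earlier in that section includes "pre-surgical laboratory examination (nutritional indexes, liver function, renal function, coagulation function, blood routine, tumor markers such as alpha-fetoprotein, etc", so its laboratory list is open-ended. Cirrhosis, fibrosis, hepatitis and Child-Pugh grade are not named as fields there, in the synopsis, or in sections 5 to 7.

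**Rationale.** Section 1 says that the snack "has been recommended by the European Society of Clinical Nutrition and Metabolism (ESPEN) for patients with cirrhosis". It also reports a meta-analysis in which "serum albumin, prealbumin, and cholinesterase levels were significantly elevated in patients with cirrhosis after implementation of LES".

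**Allocation and analysis.** Section 3.1 gives "Grouping method: non-randomized, open, enrolled according to patients' wishes". The synopsis, section 3.2 and section 10 all compare continuous measures by t-test or Mann-Whitney test, with no covariate, stratum or subgroup.

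**The concern.** The plan's own background treats cirrhosis as relevant to who needs the snack and to how albumin responds, yet the plan does not list it as something to record. In a randomised trial an unlisted prognostic factor would balance on average. Here patients choose their group, and nothing in the design balances anything.

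Cirrhosis could plausibly be related both to that choice and to albumin. If its share differs between the groups, part of any albumin difference, or part of its absence, reflects background liver disease and not the snack. A reader of the report could not tell, because the baseline table need not show cirrhosis and the test does not adjust for it.

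**Working it through.** **1. Compare rationale with data collection.** The guideline recommendation and the albumin meta-analysis in section 1 concern cirrhosis. Section 1 presents the chemoembolization albumin study as evidence in liver cancer, but its title in the reference list says the patients had liver cirrhosis. The snack composition is referenced to a source whose title also names patients with cirrhosis. Against this, no list of baseline data names cirrhosis.

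**2. Reproduce the plan's sample size.** Inputs from section 3.1: means 34.2 and 37.5 g/L, SDs 3.9 and 5.4, two-sided alpha 0.05, power 90%.
- Planned difference: 37.5 − 34.2 = 3.3 g/L.
- Average SD: √((3.9² + 5.4²)/2) = 4.71 g/L.
- An unequal-variance t-test with 44 per group has power 90.1%. The stated 88 is reproduced, so this point does not rest on an arithmetic error.

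**3. Size of a possible bias.** The documents give neither the share with cirrhosis, nor the albumin gap between patients with and without it, nor the imbalance to expect. I assume an imbalance of 10 to 30 percentage points and a gap of 2 to 5 g/L.

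Shift in the group difference = imbalance × gap. Standard error at 44 per group = 4.71 × √(2/44) = 1.004 g/L. With no true effect, the chance of a significant result in either direction is 1 − Φ(1.96 − shift/1.004) + Φ(−1.96 − shift/1.004).

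| Imbalance | Gap (g/L) | Shift (g/L) | Share of 3.3 g/L | False-positive rate |
|---|---|---|---|---|
| 10 points | 2 | 0.2 | 6% | 5.5% |
| 20 points | 3 | 0.6 | 18% | 9.2% |
| 30 points | 4 | 1.2 | 36% | 22% |
| 30 points | 5 | 1.5 | 45% | 32% |

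Last row: 1.5/1.004 = 1.494, and 1 − Φ(0.466) = 0.32.

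**4. Direction.** The gap assumes lower albumin in cirrhosis. If cirrhosis is more common in the snack group, the shift hides a benefit. If it is more common in the control group, the shift creates or inflates one. The documents do not say which is likelier.

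**5. What the proxies can do.** ICG retention, liver function, coagulation, blood count and admission-day-1 albumin are collected. Adjusting for admission albumin would remove much of a gap already present at admission. It would not remove a difference in albumin recovery after resection between livers with and without cirrhosis. The plan uses none of these variables for adjustment, and none of them identifies cirrhosis for a subgroup result.

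**The case against.** **The variable may be recoverable.** Every patient has postoperative pathology, Child-Pugh must be graded to apply the inclusion criterion, and the case form itself is not in the documents. This stands in part. A reader might infer that the confounding can never be removed, and the documents do not support that: proxies are listed, and cirrhosis could be taken from pathology or imaging. They do not say that pathology will report the background liver, however, and no analysis uses the information.

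**Broad eligibility fits the objective.** The target is patients with liver cancer after hepatectomy. Section 1 also bases the snack on the catabolism caused by resection, and on studies in liver cancer after chemoembolization, arterial chemotherapy and ablation. This stands. The plan need not restrict enrolment by cirrhosis.

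**Dilution.** A reader might infer that patients without cirrhosis dilute the effect and cost power. The documents do not support that. It requires no effect in such patients, which runs against the stated mechanism. It also requires 3.3 g/L to be the effect in cirrhosis alone, whereas section 3.1 does not give the cirrhosis status of the source patients. Adjusting for cirrhosis would not restore power lost in this way.

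**The steering is speculative, and the point derives from the missing adjustment.** Nothing shows that patients with cirrhosis will prefer the snack, and if they do, the bias runs against it. That is fair. Cirrhosis is one covariate that an adjusted analysis should contain, but the plan's own rationale makes it an obvious one, and it can be adjusted for only if it is recorded.

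**Conclusion.** The point holds as a gap in recording and adjustment. Cirrhosis is not named in any criterion or data list, groups are self-selected, and the primary comparison is unadjusted. An imbalance would therefore bias the albumin result without being seen or corrected under the analysis as written, and the listed proxies, if used, would leave residual confounding.

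The size is unknown. The range of 0.2 to 1.5 g/L (6 to 45% of the planned effect) illustrates assumed imbalances and albumin gaps. It applies to an unadjusted comparison of albumin levels, and at its low end it is negligible. The verdict does not claim that an imbalance will occur, that it would favour the snack, or that the trial is underpowered for this reason.

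**What to change.** - Add two baseline fields to section 3.2: cirrhosis yes/no, taken from the pathology report where the background liver is reported and otherwise from preoperative imaging, and the Child-Pugh grade from screening.
- Report both by group in the baseline table.
- Replace the unadjusted albumin test with a regression of postoperative albumin on group, adjusting for admission-day-1 albumin and cirrhosis.
- Show the albumin difference separately for patients with and without cirrhosis, labelled exploratory.

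The cost is one new field, one transcription of a grade already needed at screening, and a slightly larger model. Eligibility, intervention and visits stay as they are. Estimates by cirrhosis status will be imprecise with 106 patients, and adjustment for these variables does not remove other differences between self-selected groups.

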4.3 Exclusion Criteria

- 1) Failure to meet selection criteria;
- 2) Nutritional assessment as cachexia;
- 3) Presence of contraindications to enteral nutrition (EN) or EN intolerance, such as acute gastrointestinal bleeding, intestinal obstruction. (\geq grade 3, National Cancer Institute-Common Terminology Criteria for Adverse Events [NCINCI-CTCAE v 5.0]);
- 4) Simultaneous combination of malignant tumors in other parts of the body;
- 5) Combined hepatic encephalopathy or definite infection on admission;
- 6) Known refractory metabolic diseases (e.g., poorly controlled diabetes mellitus or fasting glucose \geq 10 mmol/L, hyperthyroidism, hypothyroidism, metabolic acidosis);
- 7) Decreased renal function (defined as serum creatinine Cr level \geq 176.8 μ mol/L);
- 8) Intravenous or oral nutritional supplements, such as proteins, amino acids, etc., applied within one month prior to admission to the hospital;
- 9) Patients with severe stress or severe complications such as respiratory failure with severe cardiac,

hepatic, renal and other insufficiencies;

- 10) Persons with mental and neurological disorders who are unable to cooperate with a physician;
- 11) Alzheimer's disease, cerebral atrophy, acute stage or sequelae of cerebrovascular disease, cognitive impairment;
- 12) Previously poor adherence to medication and nutritional counseling;
- 13) Critically ill and difficult to assess;
- 14) On the liver transplant waiting list or under consideration for liver transplantation, as such patients may discontinue follow-up before the end of the study;
- 15) Less than 12 months since last localized treatment (TACE or HAIC or ablative therapy);
- 16) Other circumstances that the researcher considers inappropriate for participation in the study.

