4.4 Exclusion criteria

Enrolled cases but meeting one of the following should be excluded:

- 1) Intraoperative exploration of the tumor has undergone dissemination or is unresectable;
- 2) Serious intraoperative or postoperative complications of surgical technique within 24h: bleeding or gastrointestinal leakage leading to shock;
- 3) Serious cardiac, pulmonary, cerebral or renal vital organ accidents or insufficiency during the operation or within 24h after the operation;
- 4) Postoperative pathology suggesting non-primary or metastatic hepatocellular carcinoma;
- 5) Patients in the control group who had more than 7 additional meals before bedtime;
- 6) Patients in the test group who did not have more than 7 bedtime refills during the follow-up period;
- 7) Those who voluntarily withdrew.

5. Research Methodology and Technical Approach

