7.2 Clinical outcomes

1) Post-operative complications

a) Postoperative infections: surgical site infections (SSI), remote infections (RI) and bacteremia.

SSI: Shallow/deep incision SSI and organ/space SSI were defined as redness, swelling, heat, pain, and purulent discharge observed in any incision or space operated on intraoperatively, or the need for a new drain within 30 days postoperatively.

Distant infections: including cholangitis, enteritis, pneumonia, catheter-related infections, and urinary tract infections, defined as fever greater than 38.5°C, leukocytosis, and bacteria detected in

sputum, catheter tips, and urine and feces.

Bacteremia: Bacteremia is diagnosed when a strain is cultured from a single blood culture. And when the strain is identified as coagulase-negative staphylococci, it is considered contaminating; coagulase-negative staphylococci may be considered the causative agent when isolated from two or more blood cultures.

b) Bile leakage

Fluid with a bilirubin concentration of at least three times the serum bilirubin concentration drained through an abdominal drain on or after postoperative day 3. Regardless of the initial bilirubin concentration of the drain placed through surgery, the need for radiologic (i.e., interventional drainage) or surgical intervention (i.e., relative to cesarean section) for biliary collection or biliary peritonitis is also part of the diagnosis of bile leakage.

c) Liver failure after hepatectomy

Elevated serum bilirubin concentration and elevated INR on or after postoperative day 5 compared to the previous day; or coagulation factors such as fresh frozen plasma (FFP) are required to maintain normal INR values on or after postoperative day 5 in combination with hyperbilirubinemia.

- 2) Total hospitalization cost: the total cost of the patient from admission to discharge;
- 3) Recurrence-free survival: the time from the start of the patient's hepatectomy to the first detection of tumor recurrence;
- 4) Quality of Survival: Quality of Survival was evaluated by the EORTC QLQ - HCC18 scale (Appendix 1);
- 5) Safety, diarrhea, vomiting: complaints of gastrointestinal distress that occur after the patient has initiated nutritional support therapy, with diarrhea defined as unformed stools more than three times per day.

8. Adverse Events Watch

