A data safety monitoring program will be established for clinical studies according to the level of risk. All adverse events will be recorded in detail, appropriately handled and followed up until properly resolved or stabilized, and serious adverse events and unintended events, etc., will be reported to the Ethics Committee, the competent authority, the sponsor, and the drug regulatory authority in a timely manner according to the regulations; the principal investigator will conduct a cumulative review of all adverse events on a regular basis, and convene a meeting of the investigators to assess the risks and benefits of the study, if necessary; the injuries or discomfort is no more likely and no greater in magnitude than that encountered in daily life or than that of a routine examination, and that data and safety monitoring can be accomplished by the principal investigator.

10. Statistical processing

应用 SPSS26.0 统计软件对临床数据进行描述性统计，符合正态分布的计量资料以均数±标

准差($\bar{x} \pm s$)表示, 组间采用 t 检验, 不符合正态分布的计量资料以中位数(四分位间距) [M(IQR)] 表示, 组间采用 Mann-Whitney U 检验。计数资料用百分比[n(%)]表示, 组间比较采用卡方检验, $P<0.05$ 为有显著性统计学意义。采用 STATA12.0 中的 Kaplan-Meier 法计算各组复发率及无复发生存期, log-rank 检验进行组间比较。SPSS26.0 statistical software was applied to carry out descriptive statistics of the clinical data, and the measurements that conformed to normal distribution were expressed as mean \pm standard deviation ($\bar{x} \pm s$), and t-test was used between the groups, and the measurements that did not conform to normal distribution were expressed as median (inter-quartile spacing) [M(IQR)], and Mann-Whitney U-test was used between the groups. Count data were expressed as percentages [n(%)], and the chi-square test was used for between-group comparisons, with $P<0.05$ considered statistically significant. The Kaplan-Meier method in STATA 12.0 was used to calculate the recurrence rate and recurrence-free survival in each group, and the log-rank test was used for between-group comparisons.

11. Ethical principles of clinical research

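### Previously treated patients can enter the self-chosen groups, but the plan neither specifies recording prior tumour treatment nor accounts for it in the recurrence-free survival comparison

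*Combined protocol and SAP*

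**What the plan says.** **Eligibility.** Section 4.3, item 15 (repeated in the synopsis) excludes patients with "Less than 12 months since last localized treatment (TACE or HAIC or ablative therapy"). Section 4.2, item 2 asks that the patient be "hospitalized with radical hepatectomy as the main surgical treatment", with hepatocellular carcinoma on pathology. It does not ask for a first operation or an untreated tumour. Section 4.4, item 4 removes enrolled patients with "Postoperative pathology suggesting non-primary or metastatic hepatocellular carcinoma". That concerns where the tumour came from and does not name recurrence of a primary liver tumour.

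**Data.** The baseline list in section 3.2 runs "gender, age, height, weight, BMI, ICG15min retention time, name of surgery, duration of surgery, blood loss, blood transfusion, tumor stage, NRS2002, PG-SGA", followed by the GLIM diagnosis. The synopsis list is similar. The case form described at the start of section 3.2 also names "post-surgical laboratory examination, tumor recurrence and treatment modality and patient survival, etc".

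**Endpoint and analysis.** Section 7.2 defines recurrence-free survival as "the time from the start of the patient's hepatectomy to the first detection of tumor recurrence", and section 6.5 follows it at 1, 3 and 6 months. Section 10 uses Kaplan-Meier curves and says that "the log-rank test was used for between-group comparisons". It states no stratification or covariate adjustment. Section 3.1 makes the study open and non-randomised, with group set by the patient's wish.

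**The concern.** Item 15 treats recent local tumour treatment as relevant to eligibility, yet it lets in two kinds of previously treated patient: those given TACE, HAIC or ablation more than 12 months earlier, and those with an earlier hepatectomy at any interval. Someone operated on again for a tumour that has come back may well have a different risk of a further recurrence from someone having a first resection. For both, the recurrence-free survival clock starts at the current operation.

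Randomisation would balance such patients on average. Here patients pick their group, and nothing in the design or analysis balances or adjusts for treatment history. If more of these patients choose one group, the log-rank comparison attributes their recurrence risk to the snack or to its absence. Long-term prognosis is part of the primary purpose in section 2.1, so the comparison will be read even though the endpoint is secondary.

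**Working it through.** **1. The plan's own figures.** None is given for recurrence-free survival. The only sample size is for albumin (section 3.1: 34.2 ± 3.9 v 37.5 ± 5.4 g/L, two-sided 0.05, 90% power). With SD = √((3.9² + 5.4²)/2) = 4.71 and a difference of 3.3, the noncentral-t calculation gives 44 per group, which reproduces the stated 88. The point here does not depend on it.

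**2. Who can enter, reading sections 4.2 to 4.4 together.**

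| History | Addressed by a named criterion? | Result |
|---|---|---|
| TACE, HAIC or ablation less than 12 months ago | Yes, 4.3 item 15 | Excluded |
| TACE, HAIC or ablation longer ago | Yes, by implication of item 15 | Eligible |
| Earlier hepatectomy, any interval | No | Eligible unless the investigator uses the general discretion in item 16 |

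**3. What is recorded.** The synopsis and section 3.2 lists name no prior hepatectomy, TACE, HAIC, ablation or recurrent-tumour status. In the case form, recurrence and treatment modality come after the postoperative laboratory tests and beside survival, so they read as follow-up data.

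**4. Size of confounding with no true snack effect.** Inputs, all assumed because the documents give none of them:
- 6-month recurrence in patients without prior treatment, r = 15% or 25%
- hazard in previously treated patients, k = 2 or 3 times that
- share previously treated, p, in groups A and B: 5% v 15%, or 10% v 30%

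Formulas: λ = −ln(1 − r); F(p) = p(1 − e^(−kλ)) + (1 − p)r; apparent hazard ratio, B relative to A = ln(1 − F_B)/ln(1 − F_A).

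Example with r = 15%, k = 2, 5% v 15%:
- λ = −ln(0.85) = 0.1625
- recurrence in previously treated patients = 1 − 0.85² = 0.2775
- F_A = 0.05 × 0.2775 + 0.95 × 0.15 = 0.1564
- F_B = 0.15 × 0.2775 + 0.85 × 0.15 = 0.1691
- hazard ratio = ln(0.8309)/ln(0.8436) = 0.1853/0.1700 = 1.09

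| Shares A v B | k | r = 15% | r = 25% |
|---|---|---|---|
| 10% v 10% | 2 or 3 | 1.00 | 1.00 |
| 5% v 15% | 2 | 1.09 | 1.09 |
| 5% v 15% | 3 | 1.16 | 1.15 |
| 10% v 30% | 2 | 1.17 | 1.17 |
| 10% v 30% | 3 | 1.31 | 1.29 |

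If the larger share is in the snack group, the snack looks harmful by these ratios. If it is in the control group, the snack looks protective by the reciprocals, from 1/1.09 = 0.92 to 1/1.31 = 0.76. The documents do not indicate which direction is likelier.

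**5. Set against chance.** Expected recurrences, 53 × (F_A + F_B), are about 17 to 34 in 106 patients with complete 6-month follow-up. In the 5% v 15%, k = 2 case (17 to 29 events), a 95% confidence interval spans a factor of about 2.1 to 2.6 either way. The two-sided false-positive risk rises from 5.0% to about 5.4-5.6%. In the 10% v 30%, k = 3 case it is about 9-11%.

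**The case against.** The strongest reply is that this is one covariate of unknown prevalence acting on a secondary endpoint. With so few events, sampling error exceeds the bias in every scenario above, and equal shares give none. The deeper weakness is that self-selected groups are compared without adjusting for anything: tumour stage, size and number are collected and also unused. Stratifying on treatment history alone would leave those imbalances in place. In the 5% v 15% case the previously treated stratum holds about 3 v 8 patients. All of this stands. It limits the size of the point and argues for putting treatment history into a wider adjustment. It does not justify leaving the variable unspecified.

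A reader might go further and infer that the trial will mix first and repeat resections that can never be told apart. The documents do not support either half of that. They permit repeat resections but do not indicate that any are expected. The case form is open-ended and holds the hospitalization number, so history could be looked up. Applying item 15 already means checking the date of the last TACE, HAIC or ablation, although not of an earlier hepatectomy. The name of the current operation is also recorded.

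Liver reserve is a lesser worry for albumin and the liver tests, because ICG retention and baseline albumin, cholinesterase and bilirubin are measured directly and Child-Pugh grade is limited to A and B.

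**Conclusion.** The point holds as a gap in specification that leaves a secondary comparison open to confounding. The plan admits previously treated patients, does not say that their history will be recorded, and compares self-chosen groups without using it. The apparent hazard ratio of about 1.09 to 1.31 depends wholly on the assumed recurrence rate, hazard multiple and unequal shares, and it falls to 1.00 when shares are equal. It describes all previously treated patients together; the effect of leaving hepatectomy out of item 15 cannot be estimated separately. The primary albumin calculation is untouched.

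A reader might also infer that the 12-month interval ought to cover hepatectomy. The protocol gives no rationale for item 15 from which that would follow, so it is an eligibility choice for the sponsor. What is needed is that the protocol state the choice.

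**What to change.** 1. Add prior tumour treatment (hepatectomy, TACE, HAIC, ablation, each with its last date) to the baseline list in section 3.2.
2. State in section 4 whether earlier hepatectomy is allowed, leaving the rule itself to the sponsor.
3. In section 10, prespecify that the recurrence-free survival comparison accounts for previously treated yes/no. This can be a stratified log-rank test or, better placed to deal with other imbalances, a covariate in a Cox model together with the tumour stage already collected.
4. Prespecify a sensitivity analysis in patients with no prior tumour treatment.

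The cost is one history field and a few lines of analysis text. Recording and adjusting exclude no patients. The drawback is that the previously treated stratum will probably be small and add little precision, and with about 17 to 34 events on the assumptions above a Cox model can carry only a few terms.
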